4.1.1 Inclusion Criteria

In order to qualify for enrollment in this study, each subject must meet the following inclusion criteria:

1. Capable of understanding the written informed consent, provides signed and witnessed written informed consent, and agrees to comply with protocol requirements and study-related procedures.
2. Male or female, between 18 and 65 years of age (inclusive) at the time of Screening.
3. Body mass index (BMI) between 18 and 35 kg/m² (inclusive) at the time of Screening.
4. Estimated glomerular filtration rate (eGFR) ≥ 60 mL/min/1.73 m² (Cohort 1 and 3), or eGFR ≥ 30 to < 60 mL/min/1.73 m² (Cohort 2 and 4), with eGFR calculated by the CKD-EPI equation (Section 12.1).
5. Subject has been diagnosed with ADPKD by modified Ravine criteria:
 - For subjects with family history of ADPKD, a minimum of 3 cysts per kidney by sonography or 5 cysts by CT or MRI; or
 - For subjects without family history of ADPKD, a minimum of 10 cysts per kidney by any radiologic method and exclusion of other cystic kidney diseases.

To verify the cyst count, medical records may be used in association with the Screening visit. Alternatively, in the absence of sonography or radiography evidence from medical records, subjects may be included at the discretion of the Investigator until a modified Ravine diagnosis can be confirmed through the baseline MRI assessment (see section 6.1.6).

6. Considered by the Investigator to be in good health relative to underlying CKD status and clinically stable with respect to underlying CKD, based on medical evaluation that includes medical and surgical history, as well as a complete physical examination including vital signs, ECG, and laboratory test results. A single repeat assessment is permitted for any laboratory, ECG, or vital sign parameter required for enrollment.
7. Female subjects must:
 - be non-pregnant and non-lactating;

- be either postmenopausal (defined as amenorrhea for ≥ 12 months and, if confirmation is necessary based on Investigator discretion, a confirmed follicle stimulating hormone [FSH] ≥ 40 mIU/mL), surgically sterile (defined as having undergone hysterectomy and/or bilateral oophorectomy), practice total abstinence from sexual intercourse as the preferred lifestyle (periodic abstinence is not acceptable), or agree to use an appropriate method of birth control consistently throughout the study and continue to use this method for 30 days after study drug administration.

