7. Subjects who have taken, or are expected to be taking, strong or moderate CYP3A4 or CYP2C8 inducers (e.g. barbiturates, bosentan, carbamazepine, efavirenz, enzalutamide, etravirine, modafinil, mitotane, nevirapine, oxcarbazepine, phenytoin, pioglitazone, rifabutin, rifampin, St. John's wort) within 14 days or 5 half-lives, whichever is longer, of dosing; or weak CYP3A4 or CYP2C8 inducers (e.g. armodafinil, rufinamide) within 7 days or 5 half-lives, whichever is longer, from dosing. For weak CYP3A4 or CYP2C8 inducers, medications may be allowed in consultation with the Medical Monitor (MM).
8. Subject who have a transplanted kidney, or absence of a kidney.

9. Subjects with a history of clinically significant drug or alcohol abuse within the past 5 years.
10. Subjects with a history of testing positive for hepatitis B surface antigen (HBsAg), hepatitis C (HCV), or human immunodeficiency virus (HIV).
11. Subjects who have consumed grapefruit or Seville oranges (or their juices, or foods containing their extract) from 7 days prior to the first dose of study medication and until after the final dose.
12. Subjects with clinically significant incontinence, overactive bladder, or urinary retention (e.g., benign prostatic hyperplasia).
13. Subjects with clinically significant nocturia/urgency at Screening outside of the 2 to 4 times awakening per night expected for ADPKD patients.
14. Subjects with clinically significant liver disease, or clinically significant liver function abnormalities or serology other than that expected for ADPKD with cystic liver disease at baseline.
15. Subjects with aspartate aminotransferase (AST), alanine aminotransferase (ALT), gamma-glutamyltransferase (GGT), alkaline phosphatase (ALP) or total bilirubin $\geq 1.5 \times$ upper limit of normal (ULN) at Screening. Subjects with elevated bilirubin due to Gilbert's Syndrome may be allowed at the discretion of the Investigator.
16. Subjects with any history of significant bleeding or hemorrhagic tendencies.
17. Subjects with contraindications to or interference with MRI assessments (ferromagnetic metal prostheses, aneurysm clips, severe claustrophobia, or large abdominal/back tattoos) will be excused from this procedure, but may participate in the study providing that all other eligibility criteria are met. Investigator should seek MRI safety guidance from the local MRI facility.

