4.2.1 Reasons for Withdrawal/Discontinuation

Subjects may withdraw from the study at any time and for any reason without prejudice to their future medical care by the Investigator or at the study site. Every effort should be made to keep subjects in the study and, in the case of voluntary withdrawal, to inquire as to the reason(s) for withdrawal. The reasons for subjects not completing the study will be recorded.

If a subject withdraws for any reason after having received study drug, the subject will be asked to complete ET procedures, which will be the same as those scheduled to be performed prior to discharge from the CRU on Day 8. If a subject voluntarily withdraws before receiving the study drug, no additional safety assessments or testing will be required.

A subject may be withdrawn from the study for any of the following reasons:

1. Does not meet the protocol inclusion or exclusion criteria.
2. Noncompliance with the protocol.

3. A serious or intolerable AE that, in the Investigator's opinion, requires withdrawal from the study, including but not limited to laboratory safety assessments that reveal clinically significant (CS) hematological or biochemical changes from the baseline values, other than changes that are expected for vasopressin antagonists, and symptoms or an intercurrent illness that justifies withdrawal. Mild elevations in serum creatinine or serum sodium are known pharmacodynamic effects of vasopressin antagonists like lixivaptan and are transient and reversible. Therefore, patients should not be withdrawn due to mildly elevated serum creatinine or serum sodium. Cases where eGFR has declined by 25% or more from baseline should be discussed with the Medical Monitor.
4. Lost to follow-up.
5. Other (e.g., pregnancy, development of contraindications of use of study drug).
6. The subject withdraws consent, or the Investigator or Sponsor decide to discontinue the subject's participation in the study.
7. The Investigator will also withdraw a subject if the Sponsor terminates the study.

Upon occurrence of a serious or intolerable AE, the Investigator will confer with the Sponsor. If a subject is discontinued because of an AE, the event will be followed until it is resolved or stable as determined by the Investigator. Any subject may withdraw his or her consent at any time.

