7.7.3 Safety Analyses

Clinical Laboratory Tests

All laboratory data will be summarized by renal function group and at each scheduled timepoint using descriptive statistics (n, mean, SD, median, minimum, and maximum).

The baseline value is the last value observed prior to first administration of study drug and any information taken after first administration of study drug is regarded as post baseline information. The change-from-baseline variables will be calculated as the post-baseline value minus the value at baseline. Change from baseline on continuous data will be summarized using descriptive statistics at each scheduled time point by renal function group. For categorical data, change-from-baseline will be summarized using frequency and proportion at each scheduled timepoint by renal function group.

Individual data listings of laboratory results will be presented for each subject. Values outside of the laboratory's reference range (i.e., those with low or high values) will be flagged in the laboratory listings.

For all continuous laboratory variables, a shift table comparing the baseline value (normal, low, and high) to last observation on treatment will be presented.

For urinalysis, a shift table comparing the baseline value to the maximum value will be presented by renal function group (using number of subjects with results of negative, trace, or positive).

ECGs

A listing will be provided for Investigator-identified ECG abnormalities from safety ECGs. Overall evaluation of safety ECGs will be summarized by renal function group using frequency counts and percentage of subjects as normal or abnormal, and the relevance of the abnormality will be summarized by CS or NCS.

In addition, a summary shift table comparing baseline interpretation (normal, abnormal - NCS, abnormal - CS) to the Investigator interpretation at each time point will also be presented.

Continuous ECG parameters including heart rate, ventricular rate, PR interval, QRS duration, QT interval (uncorrected), and QTcF interval will be summarized for renal function group and over each scheduled timepoint in terms of absolute values using descriptive statistics (n, mean, SD, median, minimum, and maximum).

Vital Signs

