12 APPENDICES

12.1 Appendix 1: Chronic Kidney Disease Classification Criteria

This study uses the 2009 CKD-EPI creatinine equation,¹⁶ which is recommended by the KDIGO Clinical Practice Guidelines for Management of Chronic Kidney Disease.

The CKD-EPI equation is:

$$eGFR = 141 \times \min\left(\frac{Scr}{\kappa}, 1\right)^\alpha \times \max\left(\frac{Scr}{\kappa}, 1\right)^{-1.209} \times 0.993^{Age} \times 1.018 \text{ (if female)} \times 1.159 \text{ (if black)},$$

where Scr is serum creatinine, κ is 0.7 for females and 0.9 for males, α is -0.329 for females and -0.411 for males, min indicates the minimum of Scr/ κ or 1, and max indicates the maximum of Scr/ κ or 1.

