#### 16.3. LABORATORY EVALUATIONS

Central laboratory results will be included in the reporting of this study for hematology, clinical chemistry (including liver function) and urinalysis. A list of laboratory assessments to be included in the outputs is included in Table 6-1 of the protocol. Assessment windows for laboratory evaluations are presented in Table 12-2 of the protocol. Presentations will use SI units, as provided by the laboratories.

Protocol-specified clinical laboratory tests will be summarized using descriptive statistics.

Clinical laboratory data collected during study conduct which were not required per protocol, such as for special testing to evaluate an AE, will be listed separately and not summarized.

Quantitative laboratory measurements reported as "< X", i.e. below the lower limit of quantification (BLQ), or "> X", i.e. above the upper limit of quantification (ULQ), will be converted to X for quantitative summaries, but will be presented as recorded, i.e. as "< X" or "> X", in the listings.

The following summaries will be provided for laboratory data by cohort at each scheduled timepoint:

- Actual and change from baseline (descriptive statistics n, mean, SD, median, minimum and maximum for quantitative measurements; frequency and proportion for categorical measurements)
- Shift from baseline (normal, low, high) to last observation on treatment (continuous

Author: [name]

1.0

Version Date: 25 April 2019

Version Number:

Template No: CS\_TP\_BS016 – Revision 5 Reference: CS\_WI\_BS005

Effective Date: 01Apr2018

Palladio Biosciences STATISTICAL ANALYSIS PLAN: PROTOCOL PA-102 Page 26 of 36

variables only)

- Individual data listings of laboratory results, with values outside the laboratory's
  reference range flagged as low or high. Clinical laboratory reference/normal ranges
  will be included in the listing.
- For urinalysis, shift tables comparing baseline value to maximum value (using number of subjects with results of negative, trace or positive) for categorical variables
- A listing of serum and urine pregnancy results.

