#### 16.3.1. LABORATORY REFERENCE RANGES

Quantitative laboratory measurements will be compared with the relevant laboratory reference ranges by the lab vendors and categorized as:

- Low: Below the lower limit of the laboratory reference range.
- Normal: Within the laboratory reference range (upper and lower limit included).
- High: Above the upper limit of the laboratory reference range.

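### The low/normal/high laboratory shift table cannot show worsening from a baseline already above ULN, and a transient peak can miss every laboratory summary table

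*Protocol*

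**What the plan says.** **The shift table.** Protocol 7.7.3 states that, for continuous laboratory variables, "a shift table comparing the baseline value (normal, low, and high) to last observation on treatment will be presented". Non-PK/PD SAP 16.3 keeps this rule and presents it by cohort. SAP 16.3.1 defines the top category as "High: Above the upper limit of the laboratory reference range", with no grades above it.

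**Other displays.** The same SAP section plans actual values and changes from baseline (n, mean, SD, median, minimum, maximum) by cohort and timepoint, and subject listings with out-of-range values flagged. Protocol 7.7.2 summarises change in serum creatinine, and PK/PD SAP 15.1 summarises eGFR and its change.

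**Which values count.** Under Non-PK/PD SAP 6.4, unscheduled values stay out of summary statistics and are used only where a best or worst value is needed. A valid retest takes the place of the value it repeats. Listings keep everything.

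**Who can start High.** Cohorts 2 and 4 (8 subjects each) need an eGFR of 30 to below 60. Exclusion 15 removes "Subjects with aspartate aminotransferase (AST), alanine aminotransferase (ALT), gamma-glutamyltransferase (GGT), alkaline phosphatase (ALP) or total bilirubin" at or above 1.5 × ULN at Screening, so values between 1.0 and 1.5 × ULN may enter.

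**Threshold counts.** Vital signs have markedly abnormal criteria (Non-PK/PD SAP Table 4), and urine osmolality has responder counts (PK/PD SAP 15.1). Continuous laboratory variables have neither. Protocol 4.2.1 names a size of renal change, "Cases where eGFR has declined by 25% or more from baseline should be discussed with the Medical Monitor", but neither SAP counts it.

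**The concern.** Three bins with an open top cannot register a rise from a value already in the top bin. Two groups can start there: CKD3 subjects for creatinine, because of how their cohorts are defined, and subjects admitted with mildly raised liver tests. For them, a marked worsening and an improvement that stays above ULN fall in the same cell.

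The shift also ends at the last on-treatment value. The urinalysis shift in the same section uses the maximum. Anything that peaks and settles is missed by a last-value rule, whatever the baseline.

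Safety is a primary objective, and Protocol 1.3 cites liver-safety concerns with another drug of the class. At stake is whether the report can say how many subjects per cohort had a laboratory rise of a given size.

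**Working it through.** The plan states no figure on this point, so there is none to reproduce. Its sample-size calculation (Protocol 7.4) does not bear on it.

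**1. Creatinine at the CKD3 boundary.** Inputs: the equation in Protocol Appendix 1 ("κ is 0.7 for females and 0.9 for males, α is -0.329 for females and -0.411 for males", exponent −1.209 above κ, factor 0.993 per year of age, 1.018 if female), the upper CKD3 limit of eGFR 60, and ages 18 to 65. The race factor is left out; including it raises every creatinine value. Solving for creatinine:

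Scr = κ × (141 × 0.993^age × [1.018 if female] / 60)^(1/1.209)

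| | Age 18 | Age 40 | Age 50 | Age 65 |
|---|---|---|---|---|
| Men, mg/dL | 1.64 | 1.45 | 1.36 | 1.25 |
| Women, mg/dL | 1.30 | 1.14 | 1.08 | 0.99 |

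Example, man aged 65: 0.9 × (141 × 0.633 / 60)^(0.827) = 1.25. A CKD3 subject without the race factor has a creatinine above the value shown for that age and sex.

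**2. Share of CKD3 subjects starting High.** The documents give no reference range, so ULN is an assumption. Age and eGFR (30 to 60) are taken as uniform, also an assumption.

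| Assumed ULN, mg/dL | Ages 18–65 | Ages 50–65 |
|---|---|---|
| Men 1.2 | 100% | 100% |
| Men 1.35 | 97.6% | 92.2% |
| Women 0.9 | 100% | 100% |
| Women 1.0 | 99.9% | 99.7% |
| Women 1.1 | 94.9% | 85.0% |
| Women 1.2 | 84.4% | 66.9% |

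The exceptions are mostly older women with an eGFR near 60. With a ULN of 1.1, a woman of 65 has creatinine within range at an eGFR of 52.6 or more.

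**3. What a 25% eGFR fall does.** Above κ, the creatinine ratio is (1/0.75)^(1/1.209) = 1.27. A man of 50 with eGFR 45 has creatinine 1.73 mg/dL; 1.73 × 1.27 ≈ 2.2. Both are High at any ULN in the table, so no shift is recorded.

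**4. Liver tests under the SAP 16.3.1 rule.**

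| Baseline → last, × ULN | Shift cell |
|---|---|
| 1.1 → 1.4 | High → High |
| 1.4 → 3.0 | High → High |
| 1.4 → 5.0 | High → High |
| 1.4 → 1.1 | High → High |

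**5. What the descriptive table recovers.** If one of 8 subjects goes from 1.4 to 5.0 × ULN at a scheduled visit and the other seven do not change, the change is 3.6, the mean change is 3.6/8 = 0.45 and the maximum change is 3.6. The rise is visible there.

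**6. What it does not recover.** Suppose instead that the peak is an unscheduled value, or a scheduled value followed by a lower valid retest. Protocol 6.1.5 asks for prompt confirmation of clinically significant abnormal results, so retests will occur. SAP 6.4 keeps the peak out of the descriptive statistics, and the shift uses only the last value. SAP 6.4 does name shift tables as a place where unscheduled values can feed a worst case, but this shift is not defined on the worst case. The peak then survives only in the listings, or as an adverse event if judged clinically significant.

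**The case against.** The strongest reply is that the signals are not lost. Change from baseline is shown with its maximum, eGFR change is summarised, every value is listed and flagged, and with 8 subjects per cohort one large rise is easy to see. Clinically significant results become adverse events, and treatment-emergent events are counted by cohort with percentages. This stands for rises at scheduled visits. It does not cover the route in step 6. The adverse-event route rests on investigator judgement and leaves out findings tied to the underlying disease unless they are worse than expected.

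Second, mild creatinine rise is a known, reversible effect that the protocol treats as pharmacodynamic, so analysing it on a continuous scale is reasonable. That also stands, but it gives no count of subjects.

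Third, the liver part is narrow. It needs a baseline above 1.0 and below 1.5 × ULN. The change summary for version 5 indicates that the first 8 subjects at 200 mg BID were treated before the limit was raised; until then values at or above 1.0 × ULN were excluded, with discretion for Gilbert's bilirubin. A subject who starts normal and ends high shows as Normal → High, as intended.

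Fourth, a reader might infer that the plan fails to tabulate its own safety thresholds. The documents do not support that: 1.5 and 2.0 × ULN are eligibility limits, and the 25% eGFR fall prompts a discussion. Leaving them untabulated contradicts nothing.

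Last, the output templates that accompany the SAP are not among the documents and could hold more tables than the text describes.

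**Conclusion.** The concern holds as a reporting gap. The shift table cannot show worsening from a baseline above ULN. For creatinine that probably means most CKD3 subjects: about 95–100% for ages 18 to 65 with assumed ULNs up to 1.35 mg/dL (men) and 1.1 (women), and 67–84% for women if the ULN is 1.2. These shares rest on assumed ULNs and uniform age and eGFR. For liver tests the number may be small, and the documents do not show that anyone started High. No laboratory table described in the text counts subjects by size of rise, and a transient peak can be absent from all of them.

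A reader might go further and infer that half the trial cannot contribute a creatinine shift, or that the plan would hide a liver signal. Neither follows: no ULN is given, some CKD3 subjects may start within range, and a large rise at a scheduled visit appears in the planned maximum and in the listings.

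**What to change.** 1. In Non-PK/PD SAP 16.3 add, by cohort, baseline against highest on-treatment ALT, AST, ALP, GGT and total bilirubin in multiples of ULN, for example ≤1, >1 to 1.5, >1.5 to 2, >2 to 3 and >3. The cuts at 1.5 and 2 echo the eligibility limits; the cut at 3 is a choice made here. State that unscheduled and pre-retest values count, as an exception to 6.4, and whether the Day 8 sample, taken the morning after the last dose, is on treatment.
2. In PK/PD SAP 15.1, where eGFR is assigned, add the number and percentage of subjects per cohort with an eGFR fall of 25% or more from baseline at any on-treatment assessment. Say that unscheduled values count, because 6.4 of that SAP otherwise leaves them out of summaries.

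Keep the reference-range shift as supportive. These are reporting categories only; they set no rule for managing subjects. The cost is two small descriptive tables from data already collected.

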7.7.4 Other Analyses

Listings will be provided for subject disposition, demographics, medical history, prior and concomitant medications, and summary tables will be prepared for disposition and demographics.

7.8 Data Quality Assurance

Standard operating procedures are available for all activities performed at the study sites relevant to the quality of this study. Designated study site personnel will be responsible for maintaining quality assurance and quality control to ensure that the study conduct as well as data collection and documentation are performed in compliance with the study protocol, GCP requirements, and applicable regulatory requirements.

All clinical data will undergo source document verification by the Clinical Research Associate and data review by Data Management prior to database lock. Programmed edit checks are also implemented to check for missing data, data inconsistencies, data ranges, etc. Corrections are made prior to database lock. Electronic CRFs can be printed directly from the database. Each eCRF will be reviewed and signed electronically by the Investigator.

7.8.1 Data Management

As part of the responsibilities assumed by participating in the study, the Investigator agrees to maintain adequate case histories for the subjects treated as part of the research under this protocol. The Investigator agrees to maintain accurate eCRFs and source documentation as part of the case histories. These source documents may include laboratory reports, ECGs, etc.

Investigative site personnel will enter subject data into eCRFs using the Oracle Clinical Remote Data Capture program. The analysis data sets will be a combination of these data and data from other sources (e.g., laboratory data) and follow Clinical Data Interchange Standards Consortium (CDISC) standard.

Clinical data management will be performed in accordance with applicable IQVIA standards and data cleaning procedures to ensure the integrity of the data, e.g. removing errors and inconsistencies in the data. Adverse events and concomitant medication terms will be coded using the MedDRA and World Health Organization Drug Dictionaries, respectively.

After database lock, each study site will receive all site-specific eCRF data for the study, including full discrepancy and audit history. Additionally, a copy of all of the study site's data from the study will be created and sent to the Sponsor for storage. IQVIA will maintain a duplicate copy for their records. In all cases, subject initials will not be collected or transmitted to the Sponsor.

